7.8.2 Laboratory data

The analyses of laboratory data will be descriptive in nature and will be based on BI standards "Handling, Display and Analysis of Laboratory Data" (11). Note that data from the central laboratory will be used for all displays described below, unless otherwise specified.

The analysis of continuous laboratory parameters will be based on normalised values, which means transforming to a standard unit and to a standard reference range. The last assessment before the second randomisation at visit 5 is chosen as the baseline value. The laboratory data at EoT visit are defined as EoT values. In the case that the patient is permanently discontinued BI 690517, but is continuing on empagliflozin during Treatment Period, EoT for analysis of laboratory data will be defined as the nearest scheduled lab visit on treatment of BI 690517.

Descriptive statistics of laboratory values over time and for the difference from baseline (see Section 6.7) will be based upon normalised values and provided by visit, including summaries of the last value on treatment, the minimum and maximum value on treatment.

Laboratory values will be compared to their reference ranges; a shift table will be provided for the number of patients within and outside the reference range at baseline and at the last measurement on treatment. This analysis will be based on standardized laboratory values.

Potentially clinically significant abnormalities will be identified based on BI standard rules which are based on converted values and converted reference ranges using SI lab units. These rules will be listed in the SDL appendix of the CTR. Frequency tables will summarise the number of patients with potentially clinically significant abnormalities.

Patients having an abnormal lab value at baseline will be presented separately. A separate listing will present potentially clinically significant abnormal lab values.

All individual laboratory data will be listed. Values outside the reference range will be flagged. In addition, potentially clinically significant values will be flagged in the listing.

To support analyses of liver related adverse drug effects, the frequency of patients with Aspartate Aminotransferase (AST) and/or Alanine Aminotransferase (ALT) $\geq 3x$ upper level of normal (ULN) combined with a total bilirubin $\geq 2xULN$, and the frequency of patients with AST and/or ALT $\geq 10xULN$, will be displayed. This analysis will be based on standardized laboratory values. A graphical analysis of the ALT and total bilirubin values during the on-treatment period will also be performed; the so called eDISH plot. In the graph, for each patient, the peak total bilirubin is presented as a fold increase over the ULN against the peak ALT as a fold increase over the ULN, on a log10 scale. Two reference lines, $2xULN$ for total bilirubin and $3xULN$ for ALT, are drawn onto the graph in order to divide the plane into four quadrants. Normal cases are in the lower left quadrant, potential DILI cases are in the upper right quadrant (Hy's Law quadrant), while the lower right quadrant is known as the Temple's corollary range (ALT $\geq 3xULN$ and total bilirubin $< 2xULN$).

Clinically relevant findings in laboratory data will be reported as baseline conditions (at screening) or as AEs (during the trial) if judged clinically relevant by the investigator, and will be analysed as such.

Results from the pregnancy test will only be listed.

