An individual patient will permanently discontinue BI 690517 / placebo if:

1. The patient's serum potassium measures ≥ 6.0 mmol/L by central or any local laboratory, or ≥ 5.6 mmol/L if down-titration is considered inappropriate.

¹ Where the eGFR drop occurs before the start of BI 690517 / placebo in the Treatment Period (i.e., at Visit 5), but the result is not available until after the patient starts BI 690517/placebo treatment, the patient must still permanently discontinue all randomised study treatment, including BI 690517 / placebo.

2. The patient develops Cushing's syndrome, adrenal insufficiency (including cortisol level $<18 \mu\text{g/dL}$ 30 min (± 5 min) after ACTH application) or the patient's cortisol level is $< 3 \mu\text{g/dL}$ (82.8 nmol/L) at any point in the trial. The patient must be followed according to local guidelines until resolution of the event and the event is going to be reported to the sponsor (see [section 5.2.6.1.4](#)).

An individual patient will permanently discontinue empagliflozin / placebo if:

1. Ketoacidosis is suspected.
2. Fournier's gangrene is suspected.

If empagliflozin / placebo is permanently discontinued during the Randomised Run-In period, the patient should permanently discontinue the trial. If one of the study medications (either empagliflozin/placebo or BI 690517/placebo) is permanently discontinued during the Treatment Period / after the second randomisation at Visit 5, the patient may continue to receive treatment with the other study medication and should continue with scheduled study visits according to the [Flowchart](#).

Treatment interruption

In the following case, all randomised study medication must be interrupted:

- severe SARS-COV-2 infection

In the following cases, the empagliflozin / placebo must be interrupted:

- complicated UTI
- symptomatic volume depletion

In the following cases, the BI 690517 / placebo must be interrupted:

- serum potassium $\geq 5.6 \text{ mmol/L}$ (see [section 4.2.1.1](#))
- serum potassium $\geq 5 \text{ mmol/L}$ if the patient is unable or unwilling to return to the investigational site (see [section 4.2.1.1](#))

In these cases, trial treatment could be restarted upon recovery if medically justified, please see [section 4.1.4](#).

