4.2.1.1 Management of serum potassium elevation

Increased potassium levels are not uncommon in patients with CKD and are often multifactorial in nature. A rise in serum potassium under treatment with BI 690517 cannot be excluded and therefore regular measurements of potassium levels are an integral part of the

visit schedule. For any episode of increased potassium level above 5.0 mmol/L, a clinical evaluation should be performed to make individual treatment decisions if a prompt intervention is required. For BI 690517 the dose might be adjusted to keep potassium levels in an acceptable range. The investigator should consider whether a down-titration is appropriate from a clinical perspective considering symptoms, relevant ECG changes, dynamics of potassium changes, intercurrent disorders, and lower ranges of eGFR. For detailed guidance on how to manage serum potassium elevations, please refer to [Table 4.2.1.1: 1](#).

Table 4.2.1.1: 1 Management of serum potassium

Serum Potassium	Actions (BI 690517 / placebo)
< 5.0 mmol/L	Continue on current dose if deemed appropriate (e.g. in absence of clinical symptoms or slow/small increase over time) For clinically relevant serum potassium increases to < 5.0 mmol/L, the investigator may consider interruption and/or down-titration of BI 690517 /placebo.
≥ 5.0 to <5.6 mmol/L	Option 1: Continue on current dose. Recheck K ⁺ within 72 hours. If levels continue to be ≥5.0 mmol/L, either continue dose with weekly monitoring, or follow Option 2 or Option 3. OR Option 2: Down-titration If down titration is deemed appropriate, the BI 690517 / placebo should be temporarily stopped and the next lower dose will be allocated by IRT as soon as possible. After restarting on a lower dose, investigator should recheck K ⁺ within 72 hours. If levels continue to be >5.0 mmol/L, permanently discontinue. OR Option 3: If down titration is considered inappropriate, permanently discontinue BI 690517 / placebo
≥ 5.6-< 6.0 mmol/L	Option 1: Interruption followed by down titration Study medication should be temporarily interrupted. Investigator should recheck K ⁺ every 72 hours and can restart study medication at the next lower dose once K ⁺ falls to < 5.0mmol/L. After restarting on a lower dose, investigator should recheck K ⁺ within 72 hours. If levels continue to be >5.0, permanently discontinue. OR Option 2: If down titration is considered inappropriate permanently discontinue BI 690517 / placebo

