Coagulation	Activated partial thromboplastin time (aPTT) Prothrombin Time (PT) International Normalised Ratio (INR)
Enzymes	Aspartate aminotransferase (AST) Alanine aminotransferase (ALT) Alkaline phosphatase (ALP) Gammaglutamyl transferase (GGT) Creatine kinase (CK) Lipase Amylase
Substrates	Glucose HbA1c (at Visit 1, Visit 5 and EoT) Creatinine Urea Nitrogen Uric Acid Total bilirubin Direct bilirubin Total protein Albumin Globulin Albumin / Globulin ratio C-Reactive Protein (CRP) Total cholesterol
Electrolytes	Calcium Sodium Potassium Chloride Phosphate Bicarbonate (Calculated) anion gap
Hormones	Testosterone (only for female participants at Visits 5 and EoT) Serum cortisol (at Visit 1, Visit 5 pre- and post-dose, Visit 6, Visit 7, Visit 8, Visit 9, EOT)
Serum Pregnancy test (only for female participants of childbearing potential) at Visit 1 and if urine pregnancy test is positive	Human Serum Chorionic Gonadotropin

Table 5.2.3:1 Safety laboratory tests (cont'd)

Functional lab group	Test name
Urinalysis	Urine nitrite Urine protein Urine ketone Urine bilirubin Urine Blood Urine leukocyte esterase Urine pH Specific gravity
Urine sediment (microscopic examination if erythrocytes, leukocytes nitrite or protein are abnormal in urine)	Only positive findings will be reported (e.g. presence of sediment bacteria, casts in sediment, squamous epithelial cells, erythrocytes, leukocytes)
Urine Pregnancy test (only for female participants of childbearing potential) at Visits 5, 8, 9, EoT and FUp2	Human Chorionic Gonadotropin in the urine

Urinalysis should be performed by central laboratory only. Local testing of urine should be avoided where possible, especially testing for urine glucose, as this could potentially unblind the investigator to treatment with empagliflozin.

In case qualitative urinalysis parameters are abnormal, a quantitative analysis will be performed by the central laboratory.

If blood sampling for safety at the trial site or patient's home through a member of site staff or CRO is not possible (due to a force majeure), safety lab analyses can be performed at a local lab. The results of the lab tests must be transferred to the investigator who ensures medical review. Changes in laboratory test results, if they are judged clinically relevant by the investigator, must be entered as adverse event(s). Minimum required safety lab parameters are listed in [Table 5.2.3: 2](#).

Table 5.2.3: 2 Minimum required safety laboratory tests for local labs

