All deviations from the original schedule of visits and procedures will be documented and the implications considered for the analysis of the trial data.

If blood sampling for central lab at the trial site is not possible, safety lab analyses can be performed at a local lab. The results of the lab tests must be transferred to the investigator who ensures medical review and proper documentation in the eCRF. Minimum required safety lab parameters are listed in [table 5.2.3:2](#). Urine pregnancy tests (for women of childbearing potential only, where required according to the [Flow Chart](#)) may be done at local lab / local doctor, or at home.

In the event of elevated potassium > 5 mmol/L, if the patient is unable or unwilling to return to the investigational site, the BI 690517 or matching placebo should be temporarily interrupted until the patient can return to the investigational site.

If remote visits and/or lab assessments cannot be performed within the time window for the visit, or if patient safety cannot be guaranteed, all randomised study medication needs to be interrupted until the visit and lab assessments can be conducted.

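### The laboratory displays in SAP 7.8.2 use central-laboratory data by default, so threshold counts and on-treatment extremes may omit local values, including one that ended treatment

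*SAP*

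**What the plan says.** SAP 7.8.2 sets the data source for the laboratory section: "data from the central laboratory will be used for all displays described below, unless otherwise specified". Several displays follow that depend on extreme values. By-visit descriptive statistics are given, "including summaries of the last value on treatment, the minimum and maximum value on treatment". For abnormal values, "Frequency tables will summarise the number of patients with potentially clinically significant abnormalities". The section also counts patients with raised AST or ALT with or without raised bilirubin, and plots peak ALT against peak bilirubin (eDISH). No exception to the central default appears in the visible text.

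The protocol gives local results a role in three places:

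- **Stopping.** Section 3.3.4.1 permanently discontinues BI 690517/placebo when "serum potassium measures ≥ 6.0 mmol/L by central or any local laboratory". This is not limited to disrupted visits.
- **Entry to the Treatment Period.** Inclusion criteria 13 and 14 (section 3.3.2) accept local or central potassium and eGFR.
- **Fallback testing.** Section 6.2 says: "If blood sampling for central lab at the trial site is not possible, safety lab analyses can be performed at a local lab". Section 5.2.3 gives the condition: when sampling "is not possible (due to a force majeure), safety lab analyses can be performed at a local lab". The minimum local panel (Table 5.2.3:2) includes potassium, creatinine, AST, ALT and total bilirubin, and section 6.2 requires the results to be documented in the eCRF.

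The potassium management table (section 4.2.1.1) asks for repeat measurements, for example "Investigator should recheck K ⁺ every 72 hours", but names no laboratory.

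**The concern.** The protocol treats a local potassium result as sufficient to end treatment, while the laboratory tables by default take no account of it. A patient stopped on a local value of 6.0 mmol/L or more is off drug by the next scheduled central sample, and that sample may be lower. The abnormality table and the maximum-value summary could then leave out the very result that ended treatment. A liver alert first seen on a local fallback panel could be absent from the AST/ALT/bilirubin counts and the eDISH plot in the same way.

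At stake is the objective laboratory part of a safety profile that will inform dose selection. The primary efficacy result is not touched.

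**Working it through.** The plan states no figure for laboratory abnormality counts, so there is none to reproduce. The check covers the direction of the error and then its possible size.

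**Direction.** Assume that a patient counts once if any on-treatment value meets the criterion. The detailed rules are in a sponsor standard that is not public. SAP 7 bases percentages on all patients in the set, with or without values, so the denominator does not change. Adding local values then has these effects:

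- a patient-level count rises or stays the same;
- an on-treatment maximum rises or stays the same, and a minimum falls or stays the same;
- an eDISH point moves up, moves right, or stays where it is.

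Omitting local values can therefore only understate these displays. The argument does not extend to by-visit means, changes from baseline or the shift to the last value, which could move either way.

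**Fit with SAP 6.7.** That section derives last, minimum and maximum laboratory values from all on-treatment values, whether or not they fall in a visit window. Off-schedule samples are thus meant to count, and these are the samples where a local result is most plausible. The central default in 7.8.2 works against that aim.

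**Size.** Inputs:

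- n = 120 patients per dose with both backgrounds combined (protocol 7.5: 60 per arm × 2).
- p = true share of patients with the abnormality. This is assumed at 2%, 5% or 10%.
- s = share of those patients whose abnormality appears only in local data. This is assumed at 0%, 10%, 25% or 50%.

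Expected displayed count = n × p × (1 − s). For p = 5% and s = 25%: 120 × 0.05 × 0.75 = 4.5, against 120 × 0.05 = 6.0 with all laboratories included.

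| p | s = 0% | s = 10% | s = 25% | s = 50% |
|---|---|---|---|---|
| 2% | 2.4 | 2.16 | 1.8 | 1.2 |
| 5% | 6.0 | 5.4 | 4.5 | 3.0 |
| 10% | 12.0 | 10.8 | 9.0 | 6.0 |

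Chance that at least one affected patient in a dose group of 120 is missed = 1 − (1 − p × s)^120. For p = 5% and s = 10%: 1 − 0.995^120 = 45.2%.

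| p | s = 0% | s = 10% | s = 25% | s = 50% |
|---|---|---|---|---|
| 2% | 0% | 21.4% | 45.2% | 70.1% |
| 5% | 0% | 45.2% | 77.9% | 95.2% |
| 10% | 0% | 70.1% | 95.2% | 99.8% |

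The documents give neither p nor s, so both tables are illustrations. The s = 0% column is a real possibility. A central sample may be drawn alongside the local one, or within the 7-day residual period that SAP 6.1 still counts as on treatment, and may show the same abnormality.

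**The case against.** The case for leaving 7.8.2 alone has five parts.

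1. **The default is qualified and local testing is rare.** The source sentence leaves room for exceptions, the section defers to a sponsor standard that is not public, and central testing is the protocol's rule. The fallback panel is confined to force majeure. All of this stands. It rules out reading 7.8.2 as barring local data outright, or concluding that the counts will be too low; the documents support only that they may be.

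2. **Local rechecks are not stated.** A reader might infer that potassium rechecks are done locally. The management table does not say so. The stopping rule shows only that local potassium results are expected. The eCRF requirement in section 6.2 concerns disrupted visits, and no visible text says that other local recheck values are captured as numbers.

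3. **The potassium-threshold analysis is elsewhere.** Protocol 7.2.6 plans the incidence of 5.6 mmol/L or higher and of values above 6.0 mmol/L without naming a laboratory. SAP 6.3 treats potassium as a further endpoint, and that section is not public. A reader might infer that this incidence is understated; the documents do not allow that to be judged.

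4. **Other tables carry these events.** Protocol 5.2.3 requires clinically relevant local findings to be entered as adverse events. Protocol 5.2.6.1.4 makes the liver criteria an adverse event of special interest with no central-laboratory condition. SAP 7.8.1 summarises hyperkalaemia from its own eCRF page, along with discontinuations and down-titrations. It would therefore be wrong to say that such patients vanish from safety reporting. These routes do depend on the investigator's judgement or report, however, and they are not threshold counts. SAP 7.8.2 also lists all individual laboratory data without saying whether local values are included.

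5. **Central data are the cleaner comparison.** Local assays and limits differ, and rechecks prompted by high values give some patients more chances to cross a threshold. This is a fair reason to keep the central displays. It is not a reason against adding a second set: SAP 6.7 already admits off-schedule values, and 7.8.2 already works with normalised values or multiples of the ULN.

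**Conclusion.** The concern holds in a limited form. By default, and with no visible exception, the threshold-based displays in SAP 7.8.2 leave out local values on which the protocol allows treatment to be ended. Those displays may understate abnormalities and cannot overstate them for this reason. The direction rests on counting a patient if any on-treatment value qualifies.

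The size cannot be derived from the documents. Under the assumptions shown it runs from no loss to half of the cases in a dose group. A reader might also infer that the undercount grows with dose, because protocol 4.1.2 reports a numerical rise in potassium with dose in the 28-day trial. That is plausible, but nothing in the documents shows that local-only peaks would follow the same pattern. Adverse event, special-interest and hyperkalaemia summaries limit the harm to cases that the investigator did not report.

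**What to change.** In SAP 7.8.2:

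- Keep the by-visit means, changes and all existing displays on central data.
- Add central-plus-local versions of the threshold-based displays: on-treatment maximum and minimum, potentially clinically significant abnormalities, AST/ALT/bilirubin counts and eDISH. Use eCRF-recorded local values with each laboratory's own units and ULN.
- Flag local values in the listings.
- Report by arm the number of patients who crossed a threshold, or were discontinued, on a local value alone. This count would replace the assumed s with an observed figure.

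The cost is some programming and unit/ULN harmonisation for a few analytes, with between-laboratory assay variation in the added displays. The central displays remain for the like-for-like comparison between arms. The additions can use only local results that reached the eCRF as values.

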6.2 DETAILS OF TRIAL PROCEDURES AT SELECTED VISITS

Study measurements and assessments should be performed according to the [Flow Chart](#). All assessments should be performed before study drug administration, with the exception of the post-dose PK and aldosterone profile samples.

Where the following assessments occur at a visit they should be performed in the following order:

Vital signs

ECG

Blood draws including trough PK and plasma aldosterone – other PK and plasma aldosterone samples are drawn after drug administration (see [PK and aldosterone Flow Chart](#)). Post dose-serum cortisol at Visit 5 is also drawn after drug administration.

There will be home sampling without a visit at Week -4 ('Visit' 3.1 during Randomised Run-in), Weeks 12 and 13 ('Visits' 9.1 and 9.2 respectively, during the Treatment Period), and at Weeks 16 and 17 ('Visits' FUp1.1 and FUp1.2 respectively, during the Follow-up Period). The patient will be required to collect urine samples for UACR over two consecutive days according to the [FMV and 24-hour Urine Sampling Flow Chart](#) at these times.

In this study the following visits may be performed as Telemedicine Contacts and Home Visits if all local approvals are in place. These contacts are used to help support patients with protocol procedures and compliance (see [section 6.2.1](#) and [6.2.2](#)):

- Telemedicine Contact: Visit 3
- Home Visits: Visits 4, 6, 9, FUp2

All other visits must be performed at the Investigational Site. The only exception to this is in the event of force majeure or other disrupting circumstances where physical patient visits to the sites may not be feasible or may need to be restricted to ensure patient safety. Based on a thorough assessment of the benefits and risks, the following visits may be performed at the patient's home or remotely, e.g. via telephone and/or internet-based means of communication:

- Visit 2 (first randomisation) – may be performed as a home visit only
- Visit 5 (second randomisation) – may be performed as a home visit only
- Visits 7 and 8 (Treatment Period) – may be performed as a home and/or remote visit
- EoT – may be performed as a home and/or remote visit
- FUp1 – may be performed as a home and/or remote visit

Where Visit 2 and/or Visit 5 are conducted as a home visit, eligibility assessment and randomisation must be performed prior to the visit to allow time for the study medication to be shipped to the patient's home.

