6.7 BASELINE, TIME WINDOWS AND CALCULATED VISITS

Section 2.2.2 of the CTP:

Throughout this protocol, the term “baseline” refers to the last observation prior to the first intake of trial medication, with the exception of FMV urine UACR. Baseline for the FMV urine UACR, is defined as the mean of all available samples from week -2 until prior to the first intake of trial medication. This does not include the UACR measured in spot urine at Screening.

Measurements taken after start of administration of trial treatment of BI 690517 will be considered on-treatment values based on the definition in [Section 6.1](#), and will be assigned to visits for statistical analysis, if applicable, as defined below.

Analysis of AE data, potentially clinically significant abnormal laboratory values, concomitant medication or non-drug therapies, as well as use of rescue therapy will not be based on visits. Therefore, no assignment to time windows will be necessary for such data.

The derivation of the last value, minimum value and maximum value of laboratory and vital signs data will consider all on-treatment values (whether or not selected in any time window; see [Section 6.1](#) for definition of the on-treatment period) within the period of interest; these will be derived for analysis of laboratory and vital signs data.

All other safety and efficacy measurements will be assigned to visits based on extended time windows around the planned visit dates, defined relative to the day of first trial treatment of BI 690517 (which is scheduled for Visit 5).

Repeated and unscheduled efficacy and safety measurements (except for laboratory data) will be handled similarly to scheduled measurements and will also be assigned to a time window depending upon the date of measurement. For handling of laboratory measurements see also [Section 7.8.2](#).

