7.1 DEMOGRAPHIC AND OTHER BASELINE CHARACTERISTICS

Only descriptive statistics are planned for this section of the report. The data will be summarised by dose groups of study treatment, and in total. Disease characteristics during Run-in Period will be based on available data at Screening for randomised run-in set. Baseline characteristics for randomised set will be based on available data prior to the first intake of BI 690517. Additionally, demographic and baseline characteristics will be displayed for DKD and non-DKD populations of the RS, respectively.

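### SAP 7.8.2 ties laboratory baseline to the second randomisation while SAP 6.7 and 7.1 tie it to first drug intake; if randomisation precedes the Visit 5 draw, 7.8.2 gives an old cortisol baseline and no testosterone baseline

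*SAP*

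**What the plan says.** Three SAP sections define a baseline that could apply to laboratory data.

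- SAP 7.8.2 (Laboratory data): "The last assessment before the second randomisation at visit 5 is chosen as the baseline value". The next paragraph then sends the reader elsewhere for the same quantity: "Descriptive statistics of laboratory values over time and for the difference from baseline (see Section 6.7) will be based upon normalised values".
- SAP 6.7 (Baseline, time windows and calculated visits): baseline "refers to the last observation prior to the first intake of trial medication, with the exception of FMV urine UACR". The same section refers back to 7.8.2: "For handling of laboratory measurements see also" that section.
- SAP 7.1 (Demographic and other baseline characteristics): "Baseline characteristics for randomised set will be based on available data prior to the first intake of BI 690517".

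Protocol 6.2 sets the order of events for a home Visit 5: "eligibility assessment and randomisation must be performed prior to the visit to allow time for the study medication to be shipped" to the patient. Visit 5 may be done at home only under force majeure or other disrupting circumstances; the routine home visits are 4, 6, 9 and FUp2.

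Protocol Table 5.2.3:1 gives the schedule for the tests that are not drawn at every safety laboratory visit. Serum cortisol is taken at Visit 1 and next at Visit 5 (pre- and post-dose). HbA1c is taken at Visit 1, Visit 5 and EoT. For the third it reads "Testosterone (only for female participants at Visits 5 and EoT".

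**The concern.** One set of laboratory data has two baseline rules, and each section points to the other, so neither clearly governs. Under 7.8.2, a Visit 5 pre-dose sample drawn after randomisation is not baseline. Under SAP 6.1 and 6.7 it is not on-treatment either, because that phase opens with the first BI 690517/placebo dose. The last untreated value would then have no role in the change from baseline, the shift tables or the separate display of patients abnormal at baseline. The same value would still count towards baseline characteristics under 7.1, so two tables in one report could show different baselines for one patient.

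At stake is the descriptive reading of laboratory change under an aldosterone synthase inhibitor. A Visit 1 baseline also predates empagliflozin/placebo, so a change measured from it would mix run-in and Treatment Period effects. For HbA1c this matters because half the patients start a glucose-lowering drug at Visit 2.

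**Working it through.** The plan states no figure to reproduce. The check compares the definitions with the schedule and adds up days.

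**Step 1: when the rules differ.** If the draw precedes randomisation, both rules pick the Visit 5 pre-dose value. If randomisation precedes the draw, 6.7 and 7.1 still pick it and 7.8.2 does not.

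**Step 2: whether that order can occur.**

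- At a home Visit 5 it must occur. Protocol 6.2 puts randomisation before the visit, and Protocol 6.2.2 has blood collected during it for the central laboratory.
- At a site Visit 5 it is not excluded. Protocol 6.2 requires assessments before dosing but sets no order against randomisation. Nor does eligibility force the draw to come first: inclusion criteria 13 and 14 use potassium and eGFR from the preceding 7 days, normally Visit 4. The footnote on eGFR drop in Protocol 3.3.4.1 accepts that a Visit 5 result may arrive after dosing has begun.

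**Step 3: which value 7.8.2 then selects.** Inputs: run-in 8 weeks = 56 days (Protocol 6.2.3); screening at most 21 days (Flow Chart, footnote 2); Visit 4 at Day -7 (Flow Chart).

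Age of a Visit 1 value at Visit 5 = run-in + time from Visit 1 to first randomisation = 56 + (0 to 21) = 56 to 77 days. Dividing by 7 gives 8 to 11 weeks, give or take visit windows. The upper end matches the Flow Chart's Week -11 for Visit 1.

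| Test | Scheduled before first BI 690517/placebo dose | Baseline under 6.7 / 7.1 | Baseline under 7.8.2 if randomised before the draw | Nominal age under 7.8.2 |
|---|---|---|---|---|
| Serum cortisol | Visits 1, 5 | Visit 5 | Visit 1 | 56 to 77 days |
| HbA1c | Visits 1, 5 | Visit 5 | Visit 1 | 56 to 77 days |
| Testosterone (women) | Visit 5 | Visit 5 | none | not defined |
| Other safety laboratory tests | Visits 1, 2, 4, 5 | Visit 5 | Visit 4 | about 1 week |

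**Step 4: whether another sample fills the gap.** For a delayed Visit 5, Flow Chart footnote 3 asks for a repeat safety sample for potassium and eGFR. It does not ask for cortisol, HbA1c or testosterone.

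**Step 5: effect of using the first-intake rule in 7.8.2.** The Visit 5 pre-dose draw becomes baseline whatever the time of randomisation, and every row of the table has a same-day value.

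**The case against.** The strongest reply is that 7.8.2 was never meant to discard the Visit 5 sample. It refers to 6.7 for the difference from baseline, and its own sentence can be read as shorthand for the pre-treatment Visit 5 sample. On an ordinary site visit with blood drawn first, the two sections agree. This stands as a likely account of the intent. It does not settle the text, because 6.7 refers laboratory handling back to 7.8.2, and the shorthand fails for a home Visit 5.

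The reply is also right about scope. A home Visit 5 is an exception, and all individual laboratory values are listed. Cortisol decisions in Protocol 4.2.1.3 and 5.2.5.1 rest on absolute levels and the ACTH test, and Protocol 3.2 assigns detection of cortisol increases to 24-hour urine.

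A reader might infer more than the documents support:

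- *That many site patients are affected.* The sampling chart with a pre-dose window of 45 to 1 minutes times its samples against the dose. It says nothing about order against randomisation.
- *That apparent potassium rises are biased upwards.* A Visit 4 value screened at 4.8 mmol/L or below would tend to be followed by a higher one, but in placebo patients as well, so this alone does not distort the comparison between randomised groups. SAP 6.3 also lists serum potassium among the further endpoints, and the text available does not show whether 7.8.2 governs that analysis.
- *That 6.7 is itself faulty because trial medication could mean empagliflozin at Visit 2.* SAP 6.6.2.1 names BI 690517 or placebo as the relevant intake for UACR baseline, and 7.1 names BI 690517. The UACR window in 6.7, which starts at week -2, would make no sense with an intake at week -8.

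**Conclusion.** The conflict is real and narrow. A stated rule gives a poor or undefined baseline in a situation that the protocol provides for. For each affected patient, cortisol and HbA1c baselines move back about 8 to 11 weeks to before the run-in, other safety laboratory baselines move back about one week, and a woman's testosterone change cannot be calculated.

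The documents do not say how many patients this is, and it may be few. The laboratory analyses are descriptive, without hypothesis tests. The UACR endpoints have their own baseline definition, so the dose-response analysis is unaffected.

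The conclusion rests on three assumptions: 7.8.2 is applied literally, no unscheduled pre-randomisation sample fills the gap, and the Visit 5 blood reaches the central laboratory. If a local laboratory is used instead, the minimum panel in Protocol Table 5.2.3:2 omits HbA1c and testosterone, so those two could be lost under either rule.

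**What to change.** Replace the baseline sentence in SAP 7.8.2 with: *Baseline is the last value before the first intake of BI 690517/placebo (normally the Visit 5 pre-dose sample).* This agrees with SAP 6.6.2.1 and 7.1 and with 6.7 read in context, so 6.7 needs no change.

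The cost is one sentence in the SAP and the matching derivation in the laboratory analysis data set. No new data are needed. Patients whose draw preceded randomisation keep the same baseline, and I see no downside for the others.
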